6.1. General

The present registry is intended to compile real world outcome data on the use of the MANTA Vascular Closure Device following percutaneous cardiac or peripheral procedures for large bore (10-18F ID) interventional devices. This study also fulfills EU regulatory requirements for post-market clinical follow-up.

6.2. Minimization of bias

Potential for bias during this registry has been minimized by design of a well-controlled registry, expected conduct under the terms of an approved study protocol, use of specific device indications and contraindications per IFU, careful definitions for study procedures and outcomes and prospectively defined methods of data analysis.

6.3. *Randomization*

There is no randomization in this investigation.

6.4. *Subject Replacement*

Only patients who exit the study before device implantation will be replaced by new subjects. Up to 500 subjects will receive the MANTA vascular closure device. Patients that exit the study after implantation but before study completion will not be replaced by new patients.

6.5. *Study Population*

6.5.1 Number of Subjects

Up to 500 subjects will receive 14F MANTA or 18F MANTA. The registry will consist of 2 cohorts; cohort 1 will be restricted to TAVI procedures only (with a mandatory CT at baseline and angiogram performed post MANTA closure); cohort 2 will include all other on-label CE-marked medical devices in accordance with MANTA device IFU excluding TAVI procedures.

6.5.2 MANTA Device Indications

To participate in this registry, the subject must meet all the following indications/contraindications per device IFU.

1. The 14F MANTA is indicated for closure of femoral arterial access sites following the use of 10-14F devices or sheaths (maximum OD/profile of 18F)
2. The 18F MANTA device is indicated for closure of femoral arterial access sites following the use of 15-18F devices or sheaths (maximum OD/profile of 25F).

6.5.3 MANTA Device Contraindications

Subjects are not eligible for registry participation if they meet any of the following seven contraindications: (per judgment of operator)

1. Subject with calcification severity of the access vessel
2. Subject with severe peripheral artery disease
3. Subject with puncture in the origin of the profunda femoral artery
4. Subject with sheath insertion in vessel other than the femoral artery
5. Subject with marked tortuosity of the femoral or iliac artery
6. Subject with marked obesity or cachexia (BMI >40 or <20)
7. Subject with systolic blood pressure > 180 mmHg prior

6.5.4 Subject Withdrawal or Discontinuation

Subjects must be informed about their right to withdraw from the study at any time and for any reason without sanction, penalty, or loss of benefits to which the subject is otherwise entitled. Withdrawal from the study will not jeopardize their future medical care or relationship with the investigator. Subjects will be asked to specify the reason for their termination, but have the right not to answer.

The investigator may decide to withdraw a subject from the study at any time with reasonable rationale. The subject's future care will not be influenced by a decision, voluntary or otherwise, to withdraw from the study. All reasonable efforts should be made to retain the subject in the study until completion of the study.

Reasons for subject withdrawal include, but are not limited to:

- Subject withdraws consent
- Subject refuses to continue their participation
- Subject does not meet the inclusion/exclusion criteria
- Subject is deceased (event or symptoms pertaining to outcome of death must be documented on an Adverse Event CRF)
- Subject's participation is terminated by the investigator, although the subject consented, since participation is no longer medically appropriate
- Subject is „lost to follow up“ (subject does not adhere to the scheduled follow up visits but has not explicitly requested to be withdrawn from the study)
- Site personnel should make reasonable efforts to locate and communicate with the subject in order to achieve subject compliance to the scheduled follow up visits

If a subject withdraws from the study, the site will record the subject's reasons for withdrawal on the End of Study CRF.

6.5.5 Enrollment

A patient is considered enrolled in the clinical registry after he/she has provided written informed consent, meets all device indication and contraindications and where an attempt to use the MANTA device has been made. Patients who withdraw consent or are exited by the investigator prior to implantation of the MANTA Vascular Closure Device are exited from the study without data acquisition.

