## 5 Statistical Analyses and Study Objectives

Statistical analyses will consist of descriptive statistics mean, standard deviation, median, minimum/maximum and 95% confidence intervals for continuous data and counts, proportions and 95%

confidence intervals for categorical data. Data will be qualitatively compared to VARC-2 endpoints in the literature.

All subjects with an attempted procedure where femoral artery access was initiated and MANTA device was attempted will be included in the performance and safety measures. The performance and safety endpoints will be summarized for the overall population, by cohort (TAVR vs not TAVR), and by MANTA device size (14 or 18 Fr) at a minimum. The 12M safety endpoint will also be summarized for the 12M cohort.

At the time this SAP was drafted, enrollment has closed, but follow-ups are still being completed. One subject had both sides (left and right femoral arteries) used for procedures of all enrolled subjects so summaries may be either patient based (number of participants) or device based (number of participants + 1).

The protocol specified that results will be compared to values observed in the literature. This comparison can be made by comparing the 95% confidence intervals to rates from literature. If the rate is within the 95% confidence interval, the prespecified intention is to report that a difference between the prior literature reported rate and the MARVEL study's observed rate has not been demonstrated. At a minimum, the results will be compared to the observed rates from the 2 pre-market trials, the EU Pre-Market Clinical Study (Netherlands and Italy, N=50) and the U.S. Pivotal trial (N=263 primary analysis cohort).

**Table 2.** Rates from pre-market trials for MANTA device

Trial	Time to Hemostasis (min) Mean $\pm$ SD, Median, Range, upper 97.5% confidence bound	Major Complication Rate (%) percent, 97.5% upper confidence bound	Major VARC-2 Complication Rate (%) percent	Minor Complication Rate (%) percent
EU Pre-market study (N=50)	2.38 $\pm$ 6.63 0.4 Range: 0, 37 97.5% UCB = N/A	3/50 (6%)	1/50 (2%)	0/50 (0%)
FDA PMA results (N=263)	1.09 $\pm$ 2.63 0.4 97.5% UCB = 1.41	5.3% 97.5% UCB = 8.8%	4.2%	2.7%

Additional VARC-2 complication rates have been pulled from the literature and are summarized in Table 3 below.

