## 5.5 Additional Summaries

Additional summaries will be prepared similar to the effectiveness and safety endpoints using descriptive statistics. These summaries will be prepared for the overall population, by cohort (TAVR vs not TAVR), and by MANTA device size (14 or 18 Fr) at a minimum. Some summaries will be repeated for the 12M subset as appropriate.

At a minimum the following items will be included:

1. Baseline demographics and characteristics
  - Age
  - Gender
  - BMI
  - STS score (TAVR group only)
  - Medical history (prior history of PCI, CABG, Hypertension, LVEF < 20%, kidney dysfunction (GFR < 60 umol/L), pacemaker, peripheral artery disease, stroke/CVA)
  - Medications at baseline

- i. ASCAL
- ii. Oral anticoagulants
- iii. New oral anticoagulants
- iv. Clopidogrel
- v. Heparin
- vi. Other anticoagulants

2. Procedure characteristics

- Target artery characteristics
  - i. Diameter
  - ii. Calcification
  - iii. Side (left/right/both)
  - iv. Presence of scar tissue in groin on treated side
- Procedure type
- Hemostasis time (descriptive statistics and success (<10 min) – primary performance endpoints
- MANTA procedure time
- MANTA device sizes
  - i. Instances of size mismatch (where the device size exceeds the artery size)
  - ii. Sheath-to-femoral-artery ratio
- Device deficiencies
- Procedure success (proportion of subjects with no VARC-2 major complications within 30 days)

3. 30 Day Follow-up / Exit

- Average follow-up (exit date – procedure date) in days
- Medication at each time point (during procedure, post procedure, 30 day follow-up/exit)
- Summarize type of follow-up (in person/at office or via phone call)
- Reason for study exit (as reported via eCRFs).

4. 12 Month Follow-up (for subset of 100-120 subjects)

- Average follow-up (exit day of 12 month – procedure date) in days
- Provide baseline demographics for subjects that had 12M follow-up comparing to overall population.
- Target Femoral Access Site Visual Assessment
- Adverse Events occurring on MANTA side only from day 38 to 12M visit
- Medication at each time point (12month follow-up/exit)
- Reason for study exit (as reported via eCRFs)

5. Analysis of primary and secondary safety endpoints and hemostasis by on and off-label device use. On label means meeting indications per IFU.

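### A treated subject found ineligible can be withdrawn before Day 30 yet stay in the SAP's denominator, so the Major and Minor rates, above all off-label, may be biased low

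*Protocol*

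**What the plan says.** **Protocol.** Section 6.5.2 states: "To participate in this registry, the subject must meet all the following indications/contraindications per device IFU". Section 6.5.3 makes any one of seven contraindications disqualifying and leaves them to the operator's judgment. Section 6.5.5 carries this into the definition of enrolment, which needs three things together: "A patient is considered enrolled in the clinical registry after he/she has provided written informed consent, meets all device indication and contraindications", and a procedure "where an attempt to use the MANTA device has been made". Section 6.5.6 sets the expectation of a 30-day visit for enrolled subjects.

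Section 6.5.4 lists among the withdrawal reasons "Subject does not meet the inclusion/exclusion criteria", and adds: "The investigator may decide to withdraw a subject from the study at any time with reasonable rationale". Neither statement is limited to the period before the attempt. Section 6.4 foresees exits after implantation and does not replace those subjects. Section 9.5.1 starts safety surveillance at the attempted placement and names withdrawal as one of the points at which it stops.

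**SAP.** For performance as well as safety, Section 5 sets a population without an eligibility condition: "All subjects with an attempted procedure where femoral artery access was initiated and MANTA device was attempted will be included in" these analyses. Sections 5.2 and 5.3 repeat this for the Major and Minor endpoints, both over 30 days. Section 5.5, item 5, plans "Analysis of primary and secondary safety endpoints and hemostasis by on and off-label device use". Section 6 imputes no missing outcomes and uses whatever data are available for anyone with an attempt.

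**The concern.** The two documents work with different populations. Taken literally, Protocol 6.5.5 leaves no enrolled subject who fails a criterion, whereas SAP 5.5 plans a whole analysis of off-label use. The gap matters for follow-up. The protocol offers an explicit exit for a subject who has received the device and is then found ineligible, and nothing says that such a subject must still be followed to Day 30.

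A subject who exits this way is not removed from the SAP's analysis. He or she stays in the denominator and, if no event was recorded before exit, counts as event-free although observed for only part of the 30 days. The subjects concerned are those treated outside the device's criteria, a group that a real-world registry should describe well and that may carry higher risk. The loss is concentrated in the off-label group and diluted in the overall rate.

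**Working it through.** **Step 1: follow one subject through both documents.** MANTA is attempted, a criterion is found not to be met, and the investigator withdraws the subject on Day 5 (an assumed day).

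| Question | Source | Answer |
|---|---|---|
| Is the subject enrolled? | Protocol 6.5.5 | Not on the literal wording |
| Is withdrawal after the attempt permitted? | Protocol 6.5.4 | Yes, no time limit |
| Does safety surveillance continue to Day 30? | Protocol 9.5.1 | No, it stops at withdrawal |
| Are events from Days 0 to 5 kept? | Protocol 9.5.1; SAP 6 | Yes |
| Is the subject in the safety denominator? | SAP 5, 5.2, 5.3 | Yes |
| Is an event on Days 6 to 30 counted? | SAP 6 | No: not observed, not imputed |

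Time to hemostasis is measured at the procedure, so this exit hardly touches it.

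**Step 2: size.** The plan states no figure to reproduce on this point, and SAP 4 says the sample size has no statistical basis. The number of ineligible or off-label subjects is not given, so the following is illustration.

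Inputs:
- N = 500, the maximum in Protocol 6.5.1.
- On-label Major rate p = 5.3%, from the FDA PMA row of SAP Table 2 (N = 263). As a check on this anchor, 14/263 = 5.3% has an exact upper 97.5% bound of 8.77%, which agrees with the 8.8% printed there.
- Assumed: off-label share s (2% to 20%), relative risk off-label r (1 to 3), and the share m of off-label events that fall after an early exit and are lost (25% to 50%).

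Formulas:
- Rate with full follow-up = p(1 − s) + p·s·r
- Observed rate = p(1 − s) + p·s·r·(1 − m)
- Shortfall = p·s·r·m

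| Scenario | s | r | m | Full follow-up | Observed | Events lost |
|---|---|---|---|---|---|---|
| a | 2% | 1 | 25% | 5.30% | 5.27% | 0.1 |
| b | 10% | 2 | 50% | 5.83% | 5.30% | 2.65 |
| c | 20% | 3 | 50% | 7.42% | 5.83% | 7.95 |

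Scenario b in full: on-label events 450 × 0.053 = 23.85; off-label events 50 × 0.106 = 5.30; 29.15/500 = 5.83%. With half the off-label events lost, (23.85 + 2.65)/500 = 5.30%.

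The shortfalls are 0.03, 0.53 and 1.59 percentage points. With the VARC-2 Major rate of 4.2% from the same table row as p, they are 0.02, 0.42 and 1.26 points. Within the off-label group the rate falls by the full share m: in scenario b from 10.6% to 5.3%, in c from 15.9% to 7.95%.

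For scale, the exact 95% interval for 26/500 (5.2%) is 3.4% to 7.5%. The overall shortfall lies within sampling error of about two points either way, but it always runs in the same direction.

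**The case against.** The strongest reply is that the SAP already settles the population. Sections 5, 5.2 and 5.3 keep every attempt and Section 6 uses all available data. Protocol 6.5.4 asks sites to try to keep subjects in the study, and 7.7 describes the 30-day examination for all patients, not only enrolled ones. SAP 5.5, item 3, already tabulates exit reasons and average follow-up. No hypothesis is tested, and comparison with the literature is descriptive.

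Most of this stands, and it limits the point. A reader might infer that a subject judged ineligible after a bad outcome is deleted from numerator and denominator, so that a bleed seen at closure could be erased. The documents do not support that. Safety reporting begins at the attempt, exit without data collection is confined to the time before implantation (6.5.5), and the SAP keeps recorded events. Nor do they describe any later re-reading of images to decide eligibility: CTA, angiogram and blood pressure are all assessed before closure. A literal reading of 6.5.5 might also suggest that such subjects never enter the database; no passage says so, and the planned off-label analysis suggests the opposite.

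What the reply does not meet is the shortened follow-up. The retention sentence is general and stands beside an explicit eligibility exit. Section 7.7 weakens the argument from the enrolment definition but does not bind a subject already withdrawn. The exit-reason table is not planned by label status, and nothing shows whether an eligibility exit came before or after the attempt, or whether 30-day data exist.

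**Conclusion.** The concern holds as a follow-up problem. The protocol permits a treated subject to be withdrawn for ineligibility before Day 30, and the SAP then counts that subject as event-free unless an event was recorded earlier. The bias, if present, lowers the Major and Minor rates, and does so most in the off-label group.

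Its size cannot be computed from the documents and may be negligible. The range of 0.03 to 1.6 points rests on assumed shares, risks and losses. It does not show that any such exit occurred. The point is worth correcting because the remedy is cheap and the off-label results are hard to interpret without knowing who was followed.

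**What to change.** **Protocol.** In 6.5.5, define enrolment as consent plus an attempt to use MANTA. In 6.5.4, limit the eligibility reason for withdrawal to the time before the attempt. After an attempt, record a failed criterion as a protocol deviation and keep the subject in follow-up to the 30-day visit.

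**SAP.** By on- and off-label status, report (i) the number exited as ineligible on or after the attempt and (ii) the number without 30-day follow-up. Item 5 of Section 5.5 defines on-label by indications alone, so state where a subject with a contraindication but a matching sheath size belongs. Add a sensitivity analysis of the Major and Minor rates for subjects exited as ineligible with no 30-day data and no recorded event: first leave them out of the denominator, then count them as events. Leaving them out pushes the rate up somewhat, since exits with an event remain; counting them as events is an outer bound that adds 1/500 = 0.2 points per subject overall. Subjects whose outcome is known keep that outcome.

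**Timing and cost.** SAP 5 says enrolment had closed and follow-up was still running, without saying which visits were outstanding. The enrolment wording can no longer affect who entered, and an amendment needs the full approval process of Protocol 15.1. The parts that can still act are continued follow-up and the SAP additions, which draw on the End of Study CRF. They cost a small amount of analysis and possibly a slightly less favourable safety rate.

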Clinical Design	Prospective, international, multi-center, observational, non-randomized study
Clinical Registry Purpose	The aim of this observational post market study is to compile real world outcome data on the use of the CE marked MANTA Vascular Closure Device following percutaneous cardiac or peripheral procedures for large bore (10-18F ID) interventional devices. This study also fulfills EU regulatory requirements for post-market clinical follow-up.
Indications for Use	The 14F MANTA Vascular Closure Device is indicated for closure of femoral arterial access sites following the use of 10-14F devices or sheaths (maximum OD/profile of 18F), and the 18F MANTA Vascular Closure Device is indicated for closure of femoral arterial access sites following the use of 15-18F devices or sheaths (maximum OD/profile of 25F). Procedures include transfemoral TAVI, EVAR and TEVAR; however all participants must meet indications for use and contra-indications as described in the Instructions for Use and sites must adhere to registry requirements.
Device Description	The MANTA device, developed by Essential Medical, Inc., is a VCD intended for use in catheterization laboratories following percutaneous cardiac or peripheral procedures that use the retrograde common femoral artery access route for large bore (10-18F ID) interventional devices. The function of MANTA is to percutaneously close the puncture in the artery wall (arteriotomy) through which the catheters were inserted for the procedure. The closure device consists of a hemostatic plug (collagen) in the tissue tract on the outside of the artery, which is held in place by suture linked to a small molded polymer toggle positioned inside the artery. A tiny stainless steel lock is used to secure the components in a sandwich through and on either side of the arteriotomy.

Protocol Element	Details	
Device Illustration		
Number of Subjects	
Up to 500 patients implanted with MANTA VCD which will consist of 2 cohorts.
 
 • Cohort 1 restricted to TAVI procedures (T Group) - T Group will require CT at baseline and femoral angiogram post-MANTA deployment. • Cohort 2 includes all other on-label CE-marked medical devices in accordance with MANTA device IFU excluding TAVI procedures (NT Group) - such as mechanical circulatory support (MCS), EVAR and TEVAR procedures. ET Group does not require MSCT at baseline or invasive angiography post-MANTA deployment. 	

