As the MANTA device is CE-marked, device-related AEs and SAEs will be recorded by the Sponsor as complaints, in accordance with the Sponsor's Quality System. Such complaints will be analyzed to determine if vigilance reporting is required and any required vigilance reports filed with EU competent authorities in accordance with EU medical device vigilance requirements.

9.6 *Device Deficiencies*

The Investigator will record any device deficiencies, as defined in Section 4, in the CRF. A device deficiency has occurred if a device used in the study procedure failed to meet its performance specifications whether due to mechanical failure, malfunction or defects. Device deficiencies also include use errors and inadequate labeling. This applies to:

- devices used in the subject; or
- devices in which the package was opened, but the device was not used on the subject; or
- devices with which at least one insertion attempt was made, but the device did not remain in the subject.

If the device deficiency was associated with an AE, the reporting provisions for AEs, ADEs, SAEs, SADEs and USADEs as outlined in above apply. Any device deficiency that did not lead to an AE but could have led to a SADE, if suitable action had not been taken, if intervention had not been made, or if circumstances had been less fortunate, must be reported to the Sponsor within 24 hours of the event using the CRF. Reporting to the EC and/or Competent Authority will follow EU vigilance requirements. All device deficiencies will be recorded on the CRF. Device deficiencies which could not have led to a SADE must be reported to the Sponsor within 3 business days. All devices alleged to be deficient must be returned to the Sponsor within 5 business days.

9.7. *Clinical Events Committee (CEC)*

An independent Clinical Events Committee (CEC) will be established for this study. The CEC will have at least two members who are qualified to review adverse event data from this study. The CEC will be established and operate according to a charter defined prior to the initiation of the trial. The CEC will review individual adverse events that meet the following criteria:

- AEs that are considered by the investigator to be definitely, probably or possibly device-related and will be adjudicated by CEC parallel to enrollment. Additionally, outcomes not associated with the MANTA device may also be adjudicated by CEC.

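### Protocol 6.5.5 and 6.4 set the no-data and replacement cut-off at implantation although enrolment begins at the attempt, so a subject with an attempted but not implanted MANTA may be dropped and replaced

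*Protocol*

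**What the plan says.** Two different moments serve as the cut-off.

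**The attempt.**
- Protocol 6.5.5, first sentence: a consenting patient who meets the indications and contraindications is enrolled "where an attempt to use the MANTA device has been made".
- Protocol 6.5.6: all enrolled subjects are expected to complete the 30-day visit.
- Protocol 9.5.1: safety surveillance starts at attempted placement.
- Protocol 9.6: deficiencies are recorded for "devices with which at least one insertion attempt was made, but the device did not remain in the subject".
- SAP section 5, for both performance and safety: "All subjects with an attempted procedure where femoral artery access was initiated and MANTA device was attempted will be included". SAP 5.1 to 5.3 repeat this for each endpoint.

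**Implantation.**
- Protocol 6.5.5, second sentence: the rule covers consent withdrawals and also those who "are exited by the investigator prior to implantation of the MANTA Vascular Closure Device are exited from the study without data acquisition".
- Protocol 6.4: "Only patients who exit the study before device implantation will be replaced by new subjects". Subjects who exit after implantation are not replaced.
- The target is also counted this way. Protocol 6.4 has "Up to 500 subjects will receive the MANTA vascular closure device", and the synopsis has "Up to 500 patients implanted with MANTA VCD which will consist of 2 cohorts".

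No section says which set of rules prevails.

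**The concern.** The two cut-offs leave a gap between attempt and implantation. Protocol 9.6 shows that the sponsor expects some subjects to fall there. By the attempt-based sections such a subject must be followed and analysed. By the implantation-based sections the same subject may leave with nothing recorded, and the place may go to someone else.

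An exit in this gap would not be random with respect to outcome, because the subject is there only when the device could not be placed or did not stay in place. Closure-device failure that leads to alternative treatment (other than manual compression or ballooning) is itself a Minor complication in Protocol section 4. It becomes Major if it leads to death or to life-threatening or major bleeding. Dropping such subjects takes likely events out of the numerator and the subjects out of the denominator.

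SAP section 5 compares the 95% confidence intervals with published rates, so even a few lost failures could affect how a comparison reads. The SAP's attempt-based analysis set is no protection where no data were collected, and SAP section 6 imputes nothing.

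**Working it through.** **Step 1. Trace one subject.** Take a subject who has consented, is eligible, and in whom a MANTA insertion was tried but the device did not remain.

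| Section | Rule | Result |
|---|---|---|
| Protocol 6.5.5, sentence 1 | enrolled at attempt | enrolled |
| Protocol 6.5.6 | enrolled subjects attend 30 days | follow-up expected |
| Protocol 9.5.1, 9.6 | surveillance from attempt; deficiency recorded | data expected |
| SAP 5 | attempts analysed | in analysis set |
| Protocol 6.5.5, sentence 2 | consent withdrawal or investigator exit before implantation | may leave without data |
| Protocol 6.4 | exit before implantation | replaced if exited |
| Protocol 6.4 and synopsis | 500 counted by receipt or implantation | does not count towards 500 |

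The first four rows and the last three cannot all be applied to this subject if an exit occurs. Protocol 6.5.4 lets the investigator withdraw a subject at any time with reasonable rationale, and 9.5.1 ends surveillance at withdrawal.

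**Step 2. Is there a planned figure to reproduce?** No. Protocol 8.2 and SAP section 4 give the 500 no statistical basis, and neither document states how many attempts are expected to end without implantation.

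**Step 3. Illustrate the size.** Let 500 implanted subjects be reported with x events. Let k attempted but not implanted subjects have been dropped, of whom j had the event. The rate over all attempts is (x + j)/(500 + k). Base rates come from the documents:
- Minor 2.7% (SAP Table 2, US pivotal trial): 0.027 × 500 = 13.5, taken as x = 14, so 2.8%, exact 95% CI 1.54 to 4.65%.
- Major VARC-2 4.2% (same table): 0.042 × 500 = 21, exact 95% CI 2.6 to 6.3%.
- Hemostasis Success 94.0% (EU pre-market study, Protocol section 1.4): 0.94 × 500 = 470. Each dropped attempt is assumed to be a failure, so the rate is 470/(500 + k).

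The values of k are assumptions. The complication columns take j = k, the extreme in which every dropped subject had that event. The Minor and Major columns are alternatives, because SAP 5.3 counts a subject as Minor only without a Major complication.

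| k | Minor | Major | Hemostasis Success |
|---|---|---|---|
| 0 | 14/500 = 2.8% | 21/500 = 4.2% | 94.0% |
| 1 | 15/501 = 3.0% | 22/501 = 4.4% | 93.8% |
| 5 | 19/505 = 3.8% | 26/505 = 5.1% | 93.1% |
| 10 | 24/510 = 4.7% | 31/510 = 6.1% | 92.2% |
| 15 | 29/515 = 5.6% | 36/515 = 7.0% | 91.3% |

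If only half of 10 dropped subjects had the event, the rates are 19/510 = 3.7% (Minor) or 26/510 = 5.1% (Major).

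**Step 4. Read the table.** In the extreme case, the all-attempts Minor rate passes the upper limit of the reported interval at k = 10 (4.71% against 4.65%). The Major rate is just below its limit at k = 10 (6.1% against 6.3%) and above it at k = 15. Below 10 lost cases, the true all-attempts rate stays inside the reported interval.

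**The case against.** The best defence is that the second sentence of 6.5.5 was meant for the time between consent and procedure. Protocol 7.2 takes consent before the intervention, so some patients will leave before any device is opened, and a rule for them is needed. A failed attempt is not itself an exit, and nothing tells the investigator to exit such a subject. Protocol 6.5.4 asks for a reasonable rationale and for efforts to retain subjects. Sections 6.5.6, 9.5.1 and 9.6 already call for data after an attempt, and withdrawal does not erase what has been reported. All of this stands. It shows that the intent is probably inclusive and that loss is not routine. It does not remove the conflict, because the wording chosen is implantation, in two sections and in the sample-size count.

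Several stronger readings are tempting, and the documents do not support them:
- **That failed closures in general disappear.** A device that was implanted but did not seal, or later caused bleeding or ischaemia, is past both cut-offs. It is kept and not replaced.
- **That a failure is exchanged for a success.** The replacement is a new subject who may have any outcome.
- **That Time to Hemostasis is shortened.** Its clock starts at deployment, when the sheath is withdrawn, so it is unclear what value an undeployed device would have contributed. No effect on this endpoint can be shown.
- **That withdrawal for ineligibility empties the off-label analysis.** Protocol 6.5.4 does list "Subject does not meet the inclusion/exclusion criteria" among its withdrawal reasons, but does not say that this applies to treated subjects. SAP section 6 keeps available data, and SAP 5.5 item 5 expects off-label subjects in the data set.

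**Conclusion.** The contradiction is real and should be reconciled. As written, an enrolled subject with an attempt but no implant may be exited without data and replaced, against 6.5.6, 9.5.1, 9.6 and SAP section 5. That requires a consent withdrawal or an investigator exit between attempt and implantation.

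Where it happens, the direction of bias is favourable to the device: lower complication rates, mainly Minor, and higher Hemostasis Success. The size cannot be determined. Under assumed losses of 1 to 15 cases, all with the event, a reported Minor rate of 2.8% would correspond to 3.0 to 5.6% of attempts, or a reported Major rate of 4.2% to 4.4 to 7.0%. A reported Hemostasis Success of 94.0% would correspond to 91.3 to 93.8%. With no such cases the effect is nil. These figures show sensitivity and are not evidence that any case was lost.

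**What to change.** **Protocol.** In 6.5.5 and 6.4, set the no-data and replacement cut-off at before any attempt to use the MANTA device. State that every subject with an attempt stays in data collection through the 30-day visit unless consent is withdrawn. This agrees with 6.5.6, 9.5.1 and SAP section 5.

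**SAP.** SAP section 5 says that enrolment had closed when it was drafted, so new protocol wording cannot recover a lost case. Add a disposition row with the numbers attempted, implanted, exited after an attempt without implantation, and replaced. Check it against the device-deficiency CRFs, which 9.6 requires for devices that did not remain in the subject. Count any such attempts in the endpoint denominators. Where the 30-day outcome was never collected, show the complication rates with none and with all of these subjects counted as events.

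**Cost.** The SAP change is one table row and a reconciliation against existing records. The protocol change is two sentences, but under Protocol 15.1 an amendment needs the same approvals as the original. The complication rate may become slightly less favourable. If the count is zero, the row settles the question.
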